11.0 STUDY MANAGEMENT

11.1 Institutional Review Board (IRB) Approval and Consent

It is expected that the IRB will have the proper representation and function in accordance with federally mandated regulations. The IRB should approve the consent form and protocol.

In obtaining and documenting informed consent, the investigator should comply with the applicable regulatory requirement(s), and should adhere to Good Clinical Practice (GCP) and to ethical principles that have their origin in the Declaration of Helsinki.

NU Study Number: NU 16L04
Other Study Number: CA 209-801

Before recruitment and enrollment onto this study, the patient will be given a full explanation of the study and will be given the opportunity to review the consent form. Each consent form must include all the relevant elements currently required by the FDA Regulations and local or state regulations. Once this essential information has been provided to the patient and the investigator is assured that the patient understands the implications of participating in the study, the patient will be asked to give consent to participate in the study by signing an IRB approved consent form.

Prior to a patient's participation in the trial, the written informed consent form should be signed and personally dated by the patient and by the person who conducted the informed consent discussion.

11.2 Amendments

The Principal Investigator will formally initiate all amendments to the protocol and/or informed consent. All amendments will be subject to the review and approval of the appropriate local, institutional, and governmental regulatory bodies, as well as by BMS Scientific Affairs. Amendments will be distributed by the lead institution (Northwestern) to all affiliate sites upon approval by the Northwestern University IRB.

11.3 Registration Procedures

Patients may not begin protocol treatment prior to registration. All patient registrations will be registered centrally through the Clinical Research Office at Northwestern University before enrollment to study. Please contact the assigned Quality Assurance Monitor (QAM) or email the QA Department ([contact]) for questions regarding patient registration.

Prior to registration, eligibility criteria must be confirmed by the assigned QAM. The study coordinator will screen all subjects for potential registration via the web-based application NOTIS (Northwestern Oncology Trial Information System), which is available at: <https://notis.nubic.northwestern.edu>. Please note that a username and password is required to use this program, and will be provided during site activation prior to training on the NOTIS system.

BEFORE a patient can be treated on study, please complete and submit the following items to confirm eligibility and receive an identification number:

- Patient's signed and dated informed consent form (upload to NOTIS and keep original hard copy in a secure location/study chart)
- Eligibility checklist (signed and dated by the treating physician – upload to NOTIS)
- Eligibility eCRF (complete in NOTIS)
- Copy of the pathology report (upload to NOTIS)

Training on eCRF completion will be provided at the time of site activation. Please refer to the eCRF demonstration videos on the CRO website for additional instructions on registering a patient.

The QAM will review the registration, register the patient, assign a subject identification number, and send a confirmation of registration to study personnel. Registration will then be complete and the patient may begin study treatment.

11.4 Data Submission

Once a subject is confirmed and registered to the study, eCRFs should be submitted according to the detailed data submission guidelines (provided in a separate document in NOTIS).

11.5 Data Management and Monitoring/Auditing

This study will be conducted in compliance with the Data Safety Monitoring Plan (DSMP) of the Robert H. Lurie Comprehensive Cancer Center of Northwestern University (please refer to Appendices for additional information). The level of risk attributed to this study requires high Intensity monitoring as outlined in the [DSMP](#). The assigned QAM, with oversight from the Data Monitoring Committee, will monitor this study in accordance with the study phase and risk level. Please refer to the Appendices for additional data submission instructions.

11.6 Adherence to the Protocol

Except for an emergency situation in which proper care for the protection, safety, and well-being of the study patient requires alternative treatment, the study shall be conducted exactly as described in the approved protocol.

11.6.1 Emergency Modifications

Investigators may implement a deviation from, or a change of, the protocol to eliminate an immediate hazard(s) to trial subjects without prior IRB approval.

For any such emergency modification implemented, an IRB modification form must be completed within 5 business days of making the change, and the QAM must be notified within 24 hours of such change.

11.6.2 Other Protocol Deviations

All other deviations from the protocol must be reported to the assigned QAM using the appropriate form.

A protocol deviation is any unplanned variance from an IRB approved protocol that:

- Is generally noted or recognized after it occurs.
- Has no substantive effect on the risks to research participants.
- Has no substantive effect on the scientific integrity of the research plan or the value of the data collected.
- Did not result from willful or knowing misconduct on the part of the investigator(s).

A protocol deviation may be considered an instance of Reportable New Information (RNI) if it:

- Has harmed or increased the risk of harm to one or more research participants.
- Has damaged the scientific integrity of the data collected for the study.
- Results from willful or knowing misconduct on the part of the investigator(s).
- Demonstrates serious or continuing noncompliance with federal regulations, State laws, or University policies.

11.7 Investigator Obligations

The Principal Investigator is responsible for the conduct of the clinical trial at the site in accordance with Title 21 of the Code of Federal Regulations and/or the Declaration of Helsinki. The PI is responsible for personally overseeing the treatment of all study patients. The PI must assure that all study site personnel, including sub-investigators and other study staff members, adhere to the study protocol and all FDA/GCP/NCI regulations and guidelines regarding clinical trials both during and after study completion.

The Principal Investigator at each institution or site will be responsible for assuring that all the required data will be collected, entered onto the appropriate eCRFs, and submitted within the study-specific timeframes. Periodically, monitoring visits may be conducted and

NU Study Number: NU 16L04
Other Study Number: CA 209-801

the Principal Investigator will provide access to his/her original records to permit verification of proper entry of data. The study may also be subject to routine audits by the Audit Committee, as outlined in the DSMP.

Appendix A.

Common Terminology Criteria for Adverse Events V4.0.3 (CTCAE)

The descriptions and grading scales found in the revised NCI Common Terminology Criteria for Adverse Events (CTCAE) version 4.0.3 will be utilized for adverse event reporting. (<http://ctep.cancer.gov/reporting/ctc.html>)

NU Study Number: NU 16L04
Other Study Number: CA 209-801

Appendix B – ECOG Performance Status

The Eastern Cooperative Oncology Group (ECOG) performance status scale	
Grade	Description
0	Normal activity. Fully active, able to carry on all pre-disease performance without restriction.
1	Symptoms, but ambulatory. Restricted in physically strenuous activity, but ambulatory and able to carry out work of a light or sedentary nature (e.g., light housework, office work).
2	In bed <50% of the time. Ambulatory and capable of all self-care, but unable to carry out any work activities. Up and about more than 50% of waking hours.
3	In bed >50% of the time. Capable of only limited self-care, confined to bed or chair more than 50% of waking hours.
4	100% bedridden. Completely disabled. Cannot carry on any self-care. Totally confined to bed or chair.
5	Dead.

* As published in Am. J. Clin. Oncol.: *Oken, M.M., Creech, R.H., Tormey, D.C., Horton, J., Davis, T.E., McFadden, E.T., Carbone, P.P.: Toxicity And Response Criteria Of The Eastern Cooperative Oncology Group. Am J Clin Oncol 5:649-655, 1982.* The Eastern Cooperative Oncology Group, Robert Comis M.D., Group Chair.

NU Study Number: NU 16L04
Other Study Number: CA 209-801

Appendix C – Contraception Requirements

Investigators shall counsel FOCBP and male subjects who are sexually active with FOCBP on the importance of pregnancy prevention and the implications of an unexpected pregnancy. Investigators shall advise FOCBP and male subjects who are sexually active with FOCBP on the use of highly effective methods of contraception from the time of treatment initiation to 5 months (for FOCBP) or 7 months (for males with FOCBP partners) after the last dose of nivolumab. Highly effective methods of contraception have a failure rate of < 1% per year when used consistently and correctly.

At a minimum, subjects must agree to the use of two methods of contraception, with one method being highly effective and the other method being either highly effective or less effective as listed below:

HIGHLY EFFECTIVE METHODS OF CONTRACEPTION

- a) Male condoms with spermicide
- b) Hormonal methods of contraception including combined oral contraceptive pills, vaginal ring, injectables, implants, and intrauterine devices (IUDs) such as Mirena® by FOCBP subject or male subject's FOCBP partner. Female partners of male subjects participating in the study may use hormone based contraceptives as one of the acceptable methods of contraception since they will not be receiving study drug.
- c) Nonhormonal IUDs, such as ParaGard®
- d) Tubal ligation
- e) Vasectomy.
- f) Complete Abstinence*

*Complete abstinence is defined as complete avoidance of heterosexual intercourse and is an acceptable form of contraception for all study drugs. Subjects who choose complete abstinence are not required to use a second method of contraception, but female subjects must continue to have pregnancy tests. Acceptable alternate methods of highly effective contraception must be discussed in the event that the subject chooses to forego complete abstinence.

LESS EFFECTIVE METHODS OF CONTRACEPTION

- a) Diaphragm with spermicide
- b) Cervical cap with spermicide
- c) Vaginal sponge
- d) Male Condom without spermicide*
- e) Progestin only pills by FOCBP subject or male subject's FOCBP partner
- f) Female Condom*

[figure not shown]
*A male and female condom must not be used together

Appendix D– Adverse Event Algorithms

Recommended management algorithms for suspected nivolumab related endocrinopathy, gastrointestinal toxicity, hepatotoxicity, neurologic toxicity, pulmonary toxicity, renal toxicity and skin toxicity.

Endocrinopathy Management Algorithm

[figure not shown]
Rule out non-inflammatory causes. If non-inflammatory cause, treat accordingly and continue I-O therapy. Consider visual field testing, endocrinology consultation, and imaging.

Patients on IV steroids may be switched to an equivalent dose of oral corticosteroids (e.g. prednisone) at start of tapering or earlier, once sustained clinical improvement is observed. Lower bioavailability of oral corticosteroids should be taken into account when switching to the equivalent dose of oral corticosteroids.

GI Adverse Event Management Algorithm

[figure not shown]
Rule out non-inflammatory causes. If non-inflammatory cause is identified, treat accordingly and continue I-O therapy. Opiates/narcotics may mask symptoms of perforation. Infliximab should not be used in cases of perforation or sepsis.

Patients on IV steroids may be switched to an equivalent dose of oral corticosteroids (e.g. prednisone) at start of tapering or earlier, once sustained clinical improvement is observed. Lower bioavailability of oral corticosteroids should be taken into account when switching to the equivalent dose of oral corticosteroids.

Hepatic Adverse Event Management Algorithm

Rule out non-inflammatory causes. If non-inflammatory cause, treat accordingly and continue I-O therapy. Consider imaging for obstruction.

[figure not shown]
Patients on IV steroids may be switched to an equivalent dose of oral corticosteroids (e.g. prednisone) at start of tapering or earlier, once sustained clinical improvement is observed. Lower bioavailability of oral corticosteroids should be taken into account when switching to the equivalent dose of oral corticosteroids.

*I-O therapy may be delayed rather than discontinued if AST/ALT \leq 8 x ULN or T.bili \leq 5 x ULN.

**The recommended starting dose for grade 4 hepatitis is 2 mg/kg/day methylprednisolone IV.

Neurological Adverse Event Management Algorithm

[figure not shown]
Rule out non-inflammatory causes. If non-inflammatory cause, treat accordingly and continue I-O therapy.

Patients on IV steroids may be switched to an equivalent dose of oral corticosteroids (e.g. prednisone) at start of tapering or earlier, once sustained clinical improvement is observed. Lower bioavailability of oral corticosteroids should be taken into account when switching to the equivalent dose of oral corticosteroids.

Pulmonary Adverse Event Management Algorithm

[figure not shown]
Rule out non-inflammatory causes. If non-inflammatory cause, treat accordingly and continue I-O therapy. Evaluate with imaging and pulmonary consultation.

Patients on IV steroids may be switched to an equivalent dose of oral corticosteroids (e.g. prednisone) at start of tapering or earlier, once sustained clinical improvement is observed. Lower bioavailability of oral corticosteroids should be taken into account when switching to the equivalent dose of oral corticosteroids.

Renal Adverse Event Management Algorithm

[figure not shown]
Rule out non-inflammatory causes. If non-inflammatory cause, treat accordingly and continue I-O therapy

Patients on IV steroids may be switched to an equivalent dose of oral corticosteroids (e.g. prednisone) at start of tapering or earlier, once sustained clinical improvement is observed. Lower bioavailability of oral corticosteroids should be taken into account when switching to the equivalent dose of oral corticosteroids.

Skin Adverse Event Management Algorithm

Rule out non-inflammatory causes. If non-inflammatory cause, treat accordingly and continue I-O therapy.

Patients on IV steroids may be switched to an equivalent dose of oral corticosteroids (e.g. prednisone) at start of tapering or earlier, once sustained clinical improvement is observed. Lower bioavailability of oral corticosteroids should be taken into account when switching to the equivalent dose of oral corticosteroids.

*Refer to NCI CTCAE v4 for term-specific grading criteria.

**If SJS/TEN is suspected, withhold I-O therapy and refer patient for specialized care for assessment and treatment. If SJS or TEN is diagnosed, permanently discontinue I-O therapy.

NU Study Number: NU 16L04
Other Study Number: CA 209-801

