4.2 Treatment Administration

4.2.1 Nivolumab

Treatment will be administered on an outpatient basis. Reported adverse events and potential risks are described below. No investigational or commercial agents or therapies other than those described below may be administered with the intent to treat the patient's malignancy.

During Cycle 1-4, nivolumab will be administered at a fixed dose of 240 mg intravenously over approximately 30 minutes (-5 / +15 minutes) every 14 days. Starting with Cycle 5, nivolumab will be administered at 480mg IV over 60 minutes (-10 / +15 minutes) every 28 days until disease progression, intolerable toxicity, or withdrawal of consent.

There will be no dose escalations or reductions of nivolumab allowed. Subjects may be dosed no less than 12 days or 24 days from the previous dose (for 240 mg and 480 mg doses, respectively). There are no pre-medications recommended for nivolumab on the first cycle. If an acute infusion reaction is noted, subjects should be managed according to Section 4.3.3.

Nivolumab is to be administered as a 30-minute (-5 / +15 minutes) or 60-minute (-10 / +15± minutes) IV infusion (for 240mg and 480mg respectively), using a volumetric pump with a 0.2- 1.2 micron low-protein binding in-line filter at the

NU Study Number: NU 16L04
Other Study Number: CA 209-801

protocol-specified dose. The drug can be infused undiluted or diluted so as not to exceed a total infusion volume of 120mL. It is not to be administered as an IV push or bolus injection. At the end of the infusion, flush the line with a sufficient quantity of normal saline.

Subjects will be monitored continuously for AEs while on study. Treatment delay or discontinuation will be based on specific laboratory and adverse event criteria.

Early recognition and management may mitigate severe toxicity. Evaluation and Management Guidelines were developed to assist investigators and can be found in the Investigator Brochure:

- Suspected Pulmonary Toxicity
- Diarrhea and Colitis
- Suspected Hepatotoxicity (including asymptomatic liver function tests [LFT] elevations)
- Suspected Endocrinopathy
- Nephrotoxicity

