4.3.2 Treatment discontinuation: nivolumab

Should the treating physician decide to discontinue treatment given suspicion for a drug-related side effect, the side effect should be attributed to one study drug to the best of the physician's ability. Nivolumab should be discontinued based on this attribution, and the patient must come off study treatment. The patient may not receive metformin monotherapy on-study.

Nivolumab should be discontinued permanently for the following:

- Any Grade 2 drug-related uveitis, eye pain, or blurred vision that does not respond to topical therapy and does not improve to Grade 1 severity within the re-treatment period OR requires systemic treatment
- Any Grade 3 non-skin, drug-related adverse event lasting > 7 days, with the following exceptions for laboratory abnormalities, drug-related uveitis, pneumonitis, bronchospasm, hypersensitivity reactions, infusion reactions, and endocrinopathies:
 - Grade 3 drug-related uveitis, pneumonitis, bronchospasm, hypersensitivity reaction, or infusion reaction of any duration requires discontinuation
 - Grade 3 drug endocrinopathies adequately controlled with only physiologic hormone replacement do not require discontinuation
 - Grade 3 drug-related laboratory abnormalities do not require treatment discontinuation except:
 - Grade 3 drug-related thrombocytopenia > 7 days or associated with bleeding (aside from minor bleeds \leq Grade 1) requires discontinuation
 - Any drug-related liver function test (LFT) abnormality that meets the following criteria require discontinuation:
 - AST or ALT $> 5-10 \times$ ULN for > 2 weeks
 - AST or ALT $> 10 \times$ ULN
 - Total bilirubin $> 5 \times$ ULN
 - Concurrent AST or ALT $> 3 \times$ ULN and total bilirubin $> 2 \times$ ULN
- Any Grade 4 drug-related adverse event or laboratory abnormality, except for the following events which do not require discontinuation:
 - Grade 4 neutropenia < 7 days
 - Grade 4 lymphopenia or leukopenia
 - Isolated Grade 4 amylase or lipase abnormalities that are not associated with symptoms or clinical manifestations of pancreatitis. PI and Data and Safety Monitoring Committee (DSMC) should be consulted for Grade 4 amylase or lipase abnormalities.

NU Study Number: NU 16L04
Other Study Number: CA 209-801

- Isolated Grade 4 electrolyte imbalances/abnormalities that are not associated with clinical sequelae and are corrected with supplementation/appropriate management within 72 hours of their onset

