- Grade 4 drug-related endocrinopathy adverse events, such as adrenal insufficiency, ACTH deficiency, hyper- or hypothyroidism, or glucose intolerance, which resolve or are adequately controlled with physiologic hormone replacement (corticosteroids, thyroid hormones) or glucose-controlling agents, respectively, may not require discontinuation.
- Any event that leads to interruption in dosing lasting > 4 weeks from the previous dose requires discontinuation, with the following exceptions:
 - Dosing interruptions to allow for prolonged steroid tapers to manage drug-related adverse events are allowed. Prior to re-initiating treatment in a subject with a dosing interruptions lasting > 4 weeks from the previous dose, the PI and DSMC must be consulted. Tumor assessments should continue as per protocol even if dosing is interrupted. Periodic study visits to assess safety and laboratory studies should also continue every 4 weeks or more frequently if clinically indicated during such dosing interruptions.
 - Dosing interruptions lasting > 4 weeks from the previous dose that occur for non-drug- related reasons may be allowed if approved by the PI and DSMC. Prior to re-initiating treatment in a subject with a dosing interruption lasting > 4 weeks, the PI and DSMC must be consulted. Tumor assessments should continue as per protocol even if dosing is interrupted. Periodic study visits to assess safety and laboratory studies should also continue every 4 weeks or more frequently if clinically indicated during such dosing interrupted.
 - Any adverse event, laboratory abnormality, or intercurrent illness, which in the judgment of the Investigator, presents a substantial clinical risk to the subject with continued nivolumab dosing.
 - If the patient is still receiving clinical benefit, he or she can hold drug for a maximum of 8 weeks (56 days) and subsequently continue therapy following the original treatment schedule.

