NU Study Number: NU 16L04
Other Study Number: CA 209-801

Table 4-2: Nivolumab Infusion Reactions		
NCI CTCAE Grade	Treatment	Premedication at subsequent dosing
	
subject until recovery of the symptoms
 
In case of late-occurring hypersensitivity symptoms (eg, appearance of a localized or generalized pruritus within 1 week after treatment), symptomatic treatment may be given (eg, oral antihistamine or corticosteroids)
	

Immunotherapy agents such as nivolumab are associated with AEs that can differ in severity and duration compared to other therapeutic classes of medications. Early recognition and management of AEs associated with nivolumab can mitigate severe toxicity. Corticosteroids are the primary therapy for drug-related AEs. Management algorithms have been developed to assist investigators in assessing and managing nivolumab associated AEs, which can be found in Appendix D of this protocol. The guidance provided in these algorithms should not replace the Investigator's medical judgment.

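### On its face, the Appendix D hepatic footnote permits delay of nivolumab at concurrent AST/ALT and bilirubin values for which Section 4.3.2 requires permanent discontinuation, and no sentence says which text governs

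*Combined protocol and SAP*

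**What the plan says.** Section 4.3.2 lists the events for which nivolumab is stopped for good. Its liver rule reads "Any drug-related liver function test (LFT) abnormality that meets the following criteria require discontinuation", and one of the criteria under it is "Concurrent AST or ALT $> 3 \times$ ULN and total bilirubin $> 2 \times$ ULN". That criterion has no duration condition and no delay option. The other liver criteria are AST or ALT above 10 x ULN, AST or ALT in the 5-10 x range for more than two weeks, and total bilirubin above 5 x ULN.

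Appendix D opens with "Recommended management algorithms for suspected nivolumab related endocrinopathy, gastrointestinal toxicity, hepatotoxicity" and goes on to other toxicities. The footnote to its hepatic algorithm says "I-O therapy may be delayed rather than discontinued if AST/ALT" is no more than 8 x ULN or total bilirubin is no more than 5 x ULN. The footnote does not mention concurrent elevation or Section 4.3.2.

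Three passages bear on how the two texts relate:

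- Section 4.2.1 says "Treatment delay or discontinuation will be based on specific laboratory and adverse event criteria", without naming the list that decides.
- Section 4.3.3 says that algorithms have been developed to help investigators manage nivolumab adverse events, "which can be found in Appendix D of this protocol". It calls them guidance that does not displace the investigator's medical judgment.
- Section 8.1.10 also refers the reader to Appendix D.

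None of the three says that 4.3.2 takes precedence over the appendix.

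**The concern.** Both texts address the same patients: those with drug-related liver test abnormalities (4.3.2) and those with suspected nivolumab-related hepatotoxicity (Appendix D). Both also address the same decision, whether to hold nivolumab or stop it for good. For a patient with AST 6 x ULN and bilirubin 2.5 x ULN, 4.3.2 requires the drug to be stopped, while the footnote, read alone, allows a hold. An investigator working from the algorithm could hold nivolumab and later re-dose a patient whom 4.3.2 bars permanently.

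Such values can be reached in this population. Section 3.1.5 admits patients with bilirubin up to 3 x ULN (liver metastasis or Gilbert syndrome) and AST/ALT up to 5 x ULN (liver metastasis). Some patients may therefore start with bilirubin already above 2 x ULN.

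**Working it through.** The plan states no figure to reproduce. The check sets the two rules side by side on pairs of AST/ALT and total bilirubin, both in multiples of ULN.

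**Inputs**

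- Stop rule (4.3.2): AST/ALT > 10; or bilirubin > 5; or AST/ALT > 3 together with bilirubin > 2. The criterion of more than two weeks at 5-10 x is left out, so every pair is judged on the day it occurs.
- Delay rule (Appendix D footnote): AST/ALT ≤ 8 *or* bilirubin ≤ 5. It is tested literally and, more favourably to the plan, with *and* in place of *or*.
- Assumed start of the flowchart box: AST/ALT > 5 or bilirubin > 3. The box is not shown. These values come from the Amendment 3 entry in Appendix E and serve only as an assumption.

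**Example pairs**

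| AST/ALT | Bilirubin | 4.3.2 | Footnote, literal *or* | Footnote, *and* | In assumed box |
|---|---|---|---|---|---|
| 2.5 | 1.5 | no stop | delay | delay | no |
| 3.5 | 2.5 | stop (concurrent) | delay | delay | no |
| 4 | 3.5 | stop (concurrent) | delay | delay | yes, by bilirubin |
| 6 | 1 | no stop | delay | delay | yes, by AST/ALT |
| 6 | 2.5 | stop (concurrent) | delay | delay | yes, by AST/ALT |
| 8 | 5 | stop (concurrent) | delay | delay | yes, by both |
| 12 | 1.5 | stop (> 10) | delay | not covered | yes, by AST/ALT |
| 6 | 6 | stop (> 5, and concurrent) | delay | not covered | yes, by both |

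**Region of overlap**

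With *and*, the stop and delay rules are both met where 3 < AST/ALT ≤ 8 and 2 < bilirubin ≤ 5. On a grid in steps of 0.5 x ULN this is 10 AST/ALT values (3.5 to 8.0) by 6 bilirubin values (2.5 to 5.0), so 10 × 6 = 60 points. All of them are stops under 4.3.2 through the concurrent criterion alone.

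Restricting to the assumed box removes pairs with AST/ALT ≤ 5 and bilirubin ≤ 3. That is 4 AST/ALT values (3.5 to 5.0) by 2 bilirubin values (2.5 and 3.0), or 8 points, which leaves 60 − 8 = 52. The assumption trims one corner of the region and does not remove the overlap. These counts describe the shape of the overlap only. They say nothing about how many patients would fall in it.

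**Where a hold could lead to re-dosing**

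Section 4.3.2 also says "Any event that leads to interruption in dosing lasting > 4 weeks from the previous dose requires discontinuation", subject to exceptions. In Cycles 1-4 doses are 14 days apart, so a hold of up to 28 − 14 = 14 days past the due date stays within four weeks of the previous dose and does not trigger this rule. Once doses are 28 days apart, from Cycle 5, the margin is 28 − 28 = 0 days, so any real delay brings the rule in. A short hold that no other rule catches is therefore mainly a matter for Cycles 1-4.

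**The case against.** The strongest reply is that a permission does not contradict a requirement. Section 4.3.2 says that discontinuation is required. Appendix D is headed as recommended, says *may*, and is described in 4.3.3 as guidance. An investigator who stops at 6 x with 2.5 x complies with both texts, and one who delays breaches 4.3.2. Section 11.6 requires the study to be run exactly as the approved protocol describes. The footnote can also be read as softening only its own flowchart box. On the assumed thresholds, that box is stricter for a single analyte than 4.3.2, and the footnote's bilirubin cap of 5 x equals the 4.3.2 bilirubin threshold. Most of this stands, and a careful reader would probably infer that 4.3.2 governs. But the inference is left to the reader. Appendix D is itself part of the approved protocol, its footnote speaks directly to delay versus discontinuation, and the sentence in 4.3.3 that limits the algorithms defers to the investigator's judgment and not to 4.3.2.

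Existing controls also count. Section 7.2.5 uses the same thresholds of 3 x and 2 x and calls for medical-monitor review, with reporting within 24 hours if the cause is unknown or attributed to the product. Section 4.3.1 bars re-dosing until recovery to Grade 1 or baseline. The four-week rule covers longer holds, subject to its exceptions. These lower the risk, but none says whether a recovered patient who met the concurrent criterion may be re-dosed.

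Three stronger readings are tempting and are not supported:

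- A reader might infer from the literal *or* that the footnote permits delay at AST/ALT 12 x or bilirubin 6 x. That depends on one loose word, and with *and* those pairs are not covered.
- A reader might see a second conflict with "AST or ALT $> 5-10 \times$ ULN for > 2 weeks", because the footnote sets no time limit. The two can be read in sequence, delay first and then discontinuation under 4.3.2 after two weeks, so this is no conflict.
- A reader might conclude that the algorithm as a whole omits concurrent elevation. The flowchart is not shown, so only the footnote's sentence can be judged.

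**Conclusion.** The point holds as a minor safety-consistency correction. For drug-related AST/ALT above 3 and up to 8 x ULN with total bilirubin above 2 and up to 5 x ULN, 4.3.2 requires permanent discontinuation while the footnote's visible sentence allows delay, even on the reading of *or* most favourable to the plan. If the unseen box starts at AST/ALT above 5 x or bilirubin above 3 x, the overlap is the part of that region above either threshold. No sentence ranks the two texts, although their wording points to 4.3.2.

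The documents do not support the claim that the plan intends patients who meet a 4.3.2 criterion to be re-dosed, and they give no basis for estimating how many patients could be affected. The Simon design is unaffected.

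**What to change.** Add one sentence to the hepatic footnote in Appendix D:

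> Section 4.3.2 governs: delay is not permitted when any 4.3.2 LFT discontinuation criterion is met, including concurrent AST/ALT >3 x ULN with total bilirubin >2 x ULN.

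The footnote's thresholds can stay as they are. The cost is one sentence in an amendment, with the local, institutional, governmental and BMS Scientific Affairs review set out in Section 11.2. Sample size, visits and analyses do not change.
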